Our lab group has demonstrated that hypoxemia increases blood flow through intrapulmonary arteriovenous anastomoses (IPAVA) in healthy and subjects with COPD ([name], Duke & Elliott J Physiol, 2015; Norris et al Exp Physiol, 2016). When these subjects breathe 100% O2 it prevents or reduces blood flow through IPAVA. This suggests that hypoxemia per se induces blood flow through IPAVA. The blood flow through IPAVA and presence of a PFO is also associated with increased risk of stroke and/or transient ischemic attack (Duke, Elliott, [name] Echocardiography 2015). In addition, an atrial septal defect (ASD) is a hole within the interatrial septum, and is considered a congenital heart defect. An ASD is typically larger than a PFO, and thus, the symptoms may be worse in those with an ASD, compared to those with a PFO. Thus, some hypoxemic patients who have had a stroke or transient ischemic attack, who also have a PFO/ASD may undergo surgical closure of their PFO/ASD to prevent subsequent neurological sequelae. This surgical closure may also prevent the hypoxemia thereby reducing or preventing blood flow through IPAVA. Of note, blood flow through IPAVA has been demonstrated to be strongly correlated with TIA and/or stroke and has not previously been taken into consideration in randomized clinical trials mentioned below (Abushora et al JASE, 2013).

Three randomized clinical trials have determined that PFO closure is not superior to regular medical management, for the prevention of subsequent stroke and/or TIA. Nevertheless, the American Heart Association still recommends that "in patients with cryptogenic [unexplained] TIA or stroke, a PFO, and DVT, guidelines from the American College of Chest Physicians currently recommend vitamin K antagonist therapy for 3 months and consideration of PFO closure rather than no vitamin K antagonist therapy or aspirin therapy." (Whitlock et al., CHEST 2012; 141(2)(Suppl):e576S—e600S, Kernan et al., Stroke. 2014;45:2160-2236). Additionally, in the largest single center retrospective study performed to date, PFO closure for the purpose of preventing hypoxemia was found to result in "improvement in echocardiographic evidence of right to left shunt, New York Heat Association functional class, and oxygen requirement." (Fenster et al Am J Cardiol 2013).

Thus, PFO/ASD closure remains a potentially beneficial option for both hypoxemic and stroke/TIA patients.

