Lastly, preliminary data also suggest greater levels of plasma inflammatory mediators in subjects with a PFO and systemic inflammation is associated with increased risk of cardiovascular diseases. Importantly, exercise is known to reduce so of these systemic inflammatory mediator levels. Thus, PFO/ASD closure may allow for greater exercise capacity and a subsequent reduction in inflammation.

Thus, although a PFO has been traditionally considered to have a minimal impact of physiology and pathophysiology, emerging evidence suggests this may not be the case. Our lab is focused on understanding how and why a relatively small hole in the heart (PFO/ASD) can have a relatively large impact on cardiopulmonary and respiratory physiology.

B. Specific Aims/Study Objectives

The overarching goal of this study is to examine cardiopulmonary and respiratory physiology pre and post PFO/ASD closure in patients who are undergoing surgical closure of their PFO/ASD.

Pre and post PFO/ASD closure, we will:

- 1) Quantify pulmonary gas exchange efficiency (alveolar to arterial O2 difference) and arterial oxygenation at rest and during exercise.
- 2) Quantify aerobic exercise capacity, daily activity, six-minute walk test.
- **3**) Quantify Q_{IPAVA} at rest and assess recurrence of stroke or TIA at 3 months.
- **4)** Quantify plasma inflammatory markers (TNFa, IL-1, 6 & CRP)
- **5)** Measure hypercapnic ventilatory response
- **6)** Quantify core body temperature

Hypotheses: We hypothesize that closure of PFO/ASD will improve pulmonary gas exchange efficiency, improve exercise capacity, and reduce blood flow through PFO/ASD and IPAVA thereby preventing subsequent stroke. PFO/ASD closure will also reduce plasma inflammatory mediators, increase ventilation in response to a hypercapnic challenge, and will result in a lower core body temperature.

C. Methods, Materials and Analysis

This study will be performed over the course of 7 days at the Cardiopulmonary and Respiratory Physiology Lab at the University of Oregon. Days 1-3 are Pre-PFO/ASD closure procedure and Days 4-7 repeat all research activities beginning at 3 months post PFO/ASD closure procedure. Those cleared for exercise by their cardiologists (see recruitment below)

will participate in all aspects of the study, Days 1-7. Those *not cleared for exercise* by their cardiologists will participate in all non-exercise aspects of the study Days 1-4 [gray highlight for non-exercise subject information].

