Visit 4b (PFO/ASD Not Physically Closed/Endothelialized) (~30 min)

Visit 4a (If PFO/ASD is **physically closed/endothelialized** at 3 months per referring physician)

Subjects will undergo informed consent, fill out health history questionnaire, sign a HIPAA authorization form and perform a Modified Allen's Test (~45 min)

Subjects will be comprehensively screened for any cardiac abnormalities. Amount of blood flow travelling through the PFO/ASD and IPAVA will be graded using saline contrast echocardiography while the subject is breathing room air (PFO/ASD and IPAVA blood flow) and breathing 100% O2 (PFO/ASD blood flow only). Pulmonary artery pressure will also be measured using ultrasound. Intravenous blood draw, we will take 21mls (~2 Tablespoons) of iv blood (~1.25 hrs)

Subjects will perform pulmonary function, plethysmography and diffusing capacity (30min)

Visit 4b (If PFO/ASD is **not physically closed/endothelialized** at 3 months per referring physician)

Subjects will receive and intravenous blood draw, and we will take 21mls (~2 Tablespoons) of IV blood (30 min).

Visit 2 Pre PFO/ASD Closure Procedure (~2.5 hrs) AND:

Visit 5a (PFO/ASD Physically Closed/Endothelialized) (~2.5 hrs) OR,

Visit 5b (PFO/ASD Not Physically Closed/Endothelialized) (~2 hrs):

Visit 5a (If PFO/ASD physically closed/endothelialized) at 3 months per referring physician)

Subjects will undergo a hypercapnic breathing challenge (~1hr)

Subjects will be given an activity monitor and given instructions on how and when to use it (~30 min) (Detailed Instructions on Visit 2 ONLY. On Visit 5, they will be reminded of the instructions, with details as required)

Subjects will perform a 6 minute walk test (~15 min)

Subjects will perform a VO2max test (~30 min)

Visit 5b (If PFO/ASD **not physically closed/endothelialized** at 3 months per referring physician)

Subjects will undergo informed consent, fill out health history questionnaire, sign a HIPAA authorization form and perform a Modified Allen's Test (~45 min)

Subjects will be comprehensively screened for any cardiac abnormalities. Amount of blood flow travelling through the PFO/ASD and IPAVA will be graded using saline contrast echocardiography while the subject is breathing room air (PFO/ASD and IPAVA blood flow) and breathing 100% O2 (PFO/ASD blood flow only). Pulmonary artery pressure will also be measured using ultrasound. Intravenous blood draw, we will take 21mls (~2 Tablespoons) of iv blood (~1.25 hrs)

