
Subjects will perform pulmonary function, plethysmography and diffusing capacity (30min)

Visit 3 Pre PFO/ASD Closure Procedure (~5 hrs) AND:

Visit 6a (PFO/ASD Physically Closed/Endothelialized) (~5 hrs) OR,

Visit 6b (PFO/ASD Not Physically Closed/Endothelialized) (~2.5 hrs)

Visit 6a (If PFO/ASD physically closed/endothelialized at 3 months per referring physician)

Subjects will be instrumented with a radial artery catheter by [name], MD. An esophageal temperature probe and an iv for saline contrast injections will also be placed. (~1hr)

Arterial blood will be taken at rest while subject is breathing room air and 100% O2 for 10-20 minutes to calculate shunt fraction (~30 min).

Subjects will exercise on a cycle ergometer for 4 minutes per stage at 25, 50, 75 and 90% of VO2 max breathing room air. Subjects will take up to 15 minute breaks between exercise stages (~1.5hr)

After exercise breathing room air, subjects will take a 30-minute break. (~30min)

Subject will repeat the exercise protocol above while breathing 40% O2 (~1.5hrs); note 60% O2 is the maximal level of oxygen that can be breathed and still get metabolic data required for calculating the AaDO2.

Visit 6b (If PFO/ASD **not physically closed/endothelialized** at 3 months per referring physician)

Subjects will undergo a hypercapnic breathing challenge (~1hr)

Subjects will be given an activity monitor and given instructions on how and when to use it (~30 min) (Detailed Instructions on Visit 2 ONLY. On Visit 6b, they will be reminded of the instructions, with details as required)

Subjects will perform a 6 minute walk test (~15 min)

Subjects will perform a VO2max test (~30 min)

Visit 7a (PFO/ASD Physically Closed/Endothelialized) (~ 30 mins) OR,

Visit 7b (PFO/ASD Not Physically Closed/Endothelialized) (~ 5 hrs)

Visit 7a (If PFO/ASD physically closed/endothelialized at 3 months per referring physician)

Intravenous blood draw. We will take roughly 21 mls (~2 Tablespoons) of IV blood.

Visit 7b (If PFO/ASD **not physically closed/endothelialized** at 3 months per referring physician)

Subjects will be instrumented with a radial artery catheter by [name], MD. An esophageal temperature probe and an iv for saline contrast injections will also be placed. (~1hr)

Arterial blood will be taken at rest while subject is breathing room air and 100% O2 for 10-20 minutes to calculate shunt fraction (~30 min).

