Subjects will exercise on a cycle ergometer for 4 minutes per stage at 25, 50, 75 and 90% of VO2 max breathing room air. Subjects will take up to 15 minute breaks between exercise stages (~1.5hr)

After exercise breathing room air, subjects will take a 30-minute break. (~30min)

Subject will repeat the exercise protocol above while breathing 40% O2 (~1.5hrs); note 60% O2 is the maximal level of oxygen that can be breathed and still get metabolic data required for calculating the AaDO2.

NON-EXERCISE

What follows is a detailed description of the study days. For your convenience, please refer to Figure 2. Non-Exercise (page 5) to assist in determining the timing of study days.

Visit 1 Pre PFO/ASD Closure Procedure (~2.5hrs):

Subjects will undergo informed consent, fill out health history questionnaire and perform a Modified Allen's Test (~45 min)

Subjects will be comprehensively screened for any cardiac abnormalities. Amount of blood flow travelling through the PFO/ASD and IPAVA will be graded using saline contrast echocardiography while the subject is breathing room air (PFO/ASD and IPAVA blood flow) and breathing 100% O2 (PFO/ASD blood flow only). Pulmonary artery pressure will also be measured using ultrasound. Intravenous blood draw, we will take 21mls (~2 Tablespoons) of iv blood (~1.25 hrs)

Subjects will perform pulmonary function, plethysmography and diffusing capacity (30min)

Visit 2 Pre PFO/ASD Closure Procedure (~3 hrs):

Subjects will undergo a hypercapnic breathing challenge (~1hr)

Subjects will be given an activity monitor and given instructions on how to use it (~30 min)(Detailed Instructions on Visit 2 ONLY. On Visit 3, they will be reminded of the instructions, with details as required)

Subjects will be instrumented with a radial artery catheter by [name], MD. An esophageal temperature probe and an iv for saline contrast injections will also be placed. (~1hr).

Arterial blood will be taken at rest while subject is breathing room air and 100% O2 for 10-20 minutes (~30 min).

Visit 3a (PFO/ASD Physically Closed/Endothelialized) (~4.5 hrs) OR,

Visit 3b (PFO/ASD Not Physically Closed/Endothelialized) (~30 min)

Visit 3a (If PFO/ASD physically closed/endothelialized at 3 months per referring physician)

Subjects will be instrumented with a radial artery catheter by [name], MD. An esophageal temperature probe and an iv for saline contrast injections will also be placed. (~1hr).

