• Modified Allen's Test (Days 1, 3 & 6a OR 7b Exercise; Days 1, 2 & 3a OR 4b NON-Exercise):

This test examines collateral blood flow in the hand, and is performed on the first day and each day there is an arterial line placed. The subject clenches their fist for ~30 seconds while the radial and ulnar arteries are occluded by the investigator. The ulnar artery is released and the return of circulation (color to the hand) is examined. If the color doesn't return, then this is considered a negative test (fail). Both hands will be tested, two failures (right and left hand) is exclusionary.

• Comprehensive ultrasound screening (Days 1 & 4a OR 5b Exercise; Days 1 & 3a OR 4b NON-Exercise):

An intravenous catheter will be placed in the subject. Subjects will sit in the left lateral decubitis position for ultrasound screening. An agitated saline contrast injection will be made while transthoracic saline contrast echocardiography (TTSCE) is performed on the subject to evaluate extent of blood flow through IPAVA and PFO/ASD. This will be repeated while breathing 100% O2 for 10 minutes. Subject will be asked to perform a Valsalva maneuver while breathing room air and 100% O2. This maneuver enhances blood flow across the PFO/ASD. Multiple saline contrast injections (up to 3) may be performed to verify bubble grades/presence of a PFO/ASD.

Pulmonary Function Tests (Days 1 & 4a OR 5b Exercise; Days 1 & 3a OR 4b NON-Exercise):

• Subjects will perform standard non-invasive spirometry to measure a maximal inspiratory and expiratory flow-volume loop, forced vital capacity (FVC), forced expiratory volume in 1 sec (FEV1), and mid expiratory flow (FEF25-75%). These tests will require the subject to blow in and out of a mouthpiece connected to a computerized flowmeter (pneumotachometer). This is a routine clinical test performed in pulmonary function labs in the United States.

• Diffusing Capacity (DLCO) (Days 1 & 4a OR 5b Exercise; Days 1 & 3a OR 4b NON-Exercise):

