D. Research Population & Recruitment Methods & Compensation

1-2. Sample size, Population and Recruitment Methods:

Sample Size and Data Analyses:

Necessary sample size was determined with our primary outcome variables ($AaDO_2$, VO_{2MAX} , saline contrast bubble scores, TNFa levels) using our preliminary data, previously published work and *a priori* power analysis. Using G-Power and information about a physiologically-meaningful effect from published studies (i.e. reduction of $AaDO_2$ by 50%, VO_{2MAX} increasing by 10% and 6 min walk test increasing by 50 meters (15, 34, 41)(24, 40)(24, 40), TNF-a levels decreasing by 50%, a desired power of 0.80, and alpha (0.05), we determined that n = 8-10 individuals would be sufficient to test our hypotheses, using a repeated measures design. Thus, we are asking to recruit 20 subjects (any combination of male and female) in the event

our actual pre-to-post changes are less than expected and/or there is greater variability than our preliminary data suggest.

Mean differences in $AaDO_2$ and core body temperature between pre- and post-PFO/ASD closure will be analyzed using a repeated measures ANOVA with Tukey posttest. Mean differences in $VO_{2MAX,}$ 6 minute walk test, activity, inflammatory markers and hypercapnic ventilator response, between pre and post PFO/ASD closure will be analyzed using a paired t-test. Differences in bubble scores pre- and post-closure will be analyzed using a Mann-Whitney U test.

The population of subjects will include patients who are undergoing PFO/ASD closure at either PeaceHealth or McKenzie-Willamette Hospitals. Subjects will be identified by [name] (PeaceHealth/Oregon Heart & Vascular Institute) and [name] (McKenzie-Willamette). These two cardiologists will only refer subjects to contact the [name] Lab for informed consent and enrollment into the study. Drs. [name] and [name] will identify potential subjects as "cleared for exercise" or "not cleared for exercise." (See statement of PHI above). Drs. [name] and [name] will not be formally engaged in the research (i.e. they will not consent subjects, have access to identifiable data, etc). No research activities will take place at either hospital. Subject fliers, initial phone script and email script are attached.

3. Detailed Recruitment information:

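### The planned pre/post bubble-score comparison does not isolate intrapulmonary (IPAVA) flow: a room-air score falls when the defect closes, even if IPAVA flow is unchanged

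*Combined protocol and SAP*

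**What the plan says.** Section B (Aim 3) sets out to quantify IPAVA flow at rest. The hypotheses say that closure will "reduce blood flow through PFO/ASD and IPAVA thereby preventing subsequent stroke".

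Section C describes the resting echo in the same words for both groups. Flow is graded "while the subject is breathing room air (PFO/ASD and IPAVA blood flow) and breathing 100% O2 (PFO/ASD blood flow only". The ultrasound screening paragraph confirms the second reading: "This will be repeated while breathing 100% O2 for 10 minutes". A Valsalva maneuver is done on both gases, and of it the protocol says: "This maneuver enhances blood flow across the PFO/ASD".

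The full post-closure echo takes place at 3 months if the referring physician judges the defect closed, and otherwise at 6 months. Subjects still not closed at 6 months are excluded (Section C, special note; Table 3).

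Section D lists saline contrast bubble scores among the primary outcomes. Its whole analysis statement is that "Differences in bubble scores pre- and post-closure will be analyzed" with a Mann-Whitney U test. It names no gas condition, gives no rule for Valsalva readings and defines no comparison that separates the two sources of bubbles.

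**The concern.** Before closure the room-air grade reflects two sources. After confirmed closure it reflects, in essence, one. A pre/post comparison of that grade therefore subtracts unlike quantities, and device closure alone produces a fall. Read against the title and hypotheses, that fall could be reported as closure having reduced intrapulmonary shunting when nothing in the lung has changed.

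A better test does not cure this. A correct paired test on perfectly read room-air grades gives the same answer. (That Mann-Whitney U is an unpaired test applied to paired data is a separate matter.)

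The shunt fraction does not fill the gap. Section C says: "Arterial blood will be taken at rest while subject is breathing room air and 100% O2 for 10-20 minutes to calculate shunt fraction". On 100% O2, Section A says of IPAVA flow: "When these subjects breathe 100% O2 it prevents or reduces blood flow through IPAVA". A value obtained on that gas largely removes the flow in question.

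**Working it through.** **The plan's own figure.** Section D gives n = 8-10 (recruit 20) for power 0.80 and alpha 0.05. It states no effect size or SD for the bubble score, so this n cannot be reproduced for that outcome. Inverting a two-sided paired t-test gives a standardized change of 1.16 at n = 8 and 1.00 at n = 10. The point below does not depend on it.

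**Step 1: what each comparison measures.** Let D be defect flow before closure (0 after), and let I and I' be IPAVA flow before and after. Take the protocol's description literally, with flows adding:
- Room air: (D + I) before, I' after. Fall = D + (I - I'). If I' = I, the fall is D.
- 100% O2: D before, 0 after. Fall = D.
- Room air minus 100% O2: (D + I) - D = I before, I' - 0 = I' after. Fall = I - I', the quantity wanted.
- If a fraction r of IPAVA flow persists on 100% O2, the contrast is (1 - r)I before and (1 - r)I' after. The sign is right but the size shrinks; with r = 0.5, half of a real change is seen.

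**Step 2: an ordinal scale.** The documents give no grading scale or combination rule. Assume grades 0-5, I equally likely to be 0, 1 or 2 and unchanged by closure, and D uniform over the range shown. If the larger source sets the grade, the false room-air fall is max(0, D - I), and the contrast shows a false rise of min(D, I). If grades add with a cap at 5, the contrast is biased only when D + I exceeds 5.

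Mean false room-air fall, averaged over I = 0, 1, 2:
- Larger source, D 1-5: (3 + 2 + 1.2)/3 = 2.07
- Larger source, D 0-2: (1 + 0.33 + 0)/3 = 0.44
- Additive, capped, D 1-5: (3 + 2.8 + 2.4)/3 = 2.73

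Mean false rise in the contrast:
- Larger source, D 1-5: (0 + 1 + 1.8)/3 = 0.93
- Larger source, D 0-2: (0 + 0.67 + 1)/3 = 0.56
- Additive, capped, D 1-5: (0 + 0.2 + 0.6)/3 = 0.27
- Additive, D 1-3: 0

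**Step 3: how often this reaches significance.** Same assumptions, plus a one-grade reading error in 20% of readings; paired signed-rank test, two-sided 0.05. Ranges span repeat runs.

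| Combination rule, defect grade | Room air: false reduction, n = 8 / 10 / 20 | Contrast: false increase, n = 8 / 10 / 20 |
|---|---|---|
| Larger source, 1-5 | 86-89% / 96-97% / 100% | 41-51% / 57-70% / 92-98% |
| Larger source, 0-2 | 13% / 19% / 53% | not tabulated |
| Additive, capped at 5, 1-5 | 100% / 100% / 100% | 3-6% / 4-7% / about 14% |
| Additive, 1-3 | not tabulated | 0-2% at every n |

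**Step 4: a second model, using the planned test.** Here flows are continuous and additive, then rounded to a 0-5 grade (mean IPAVA flow 1, reading noise SD 0.5, IPAVA unchanged, suppression on 100% O2 complete or half). With mean defect flow of 1, 2 and 3, the room-air grade falls by about 1.1, 1.9-2.0 and 2.8. Mann-Whitney rejects in 53-54%, 98% and 100% of runs at n = 10, and in 90-100% at n = 20. The contrast rejects in 1-5% (Mann-Whitney) or 3-8% (signed-rank). Near the scale ceiling (defect 4, IPAVA 1.5) the contrast is biased by about -0.55 grade and rejects in 22-24% at n = 10 and 47-51% at n = 20.

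**The case against.** The strongest reply is that the design already contains the remedy. The same sentence that defines the room-air grade provides a 100% O2 grade meant to show defect flow only. It is taken at rest before and after closure, and Aim 3 concerns rest. This stands. A reader might infer that the bubble score cannot answer the IPAVA question at all, but the documents do not support that. What is missing is a defined analysis, not the resting measurement.

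A reader might also infer that subtracting the 100% O2 grade is bound to create a false increase. That follows only if the larger source alone sets the grade, a rule found nowhere in the protocol. With additive grades the artefact is small unless the scale saturates. Masking is a plausible limit, not an established failure.

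The plan also does not commit to reading a room-air fall as an IPAVA effect. The hypothesis names defect flow too, and a fall bears legitimately on that half. This is fair, but Section D offers no other comparison for the IPAVA half, so the reply does not remove the problem.

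The remedy has its own limits. Section A says only that oxygen prevents or reduces IPAVA flow, which is weaker than a defect-only reading. During exercise, echo is done on 21% and 40% O2, so no 100% O2 reference exists there.

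**Conclusion.** The concern holds for the analysis as written. A pre/post room-air bubble score measures total right-to-left flow. With IPAVA flow unchanged, it falls by the defect component under additive flow, and by any excess of defect over IPAVA grade if the larger source sets the grade. The direction follows from the protocol's own description and from confirmed closure before the post-closure echo.

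The size is uncertain. False reductions occur in about 13% to 100% of simulated trials at n = 8 to 20, under assumed grade distributions and combination rules that the documents do not supply. The figures are illustrative.

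The resting room-air versus 100% O2 contrast can address Aim 3 approximately. It requires that defect flow does not mask or saturate the room-air grade and that oxygen suppresses a useful share of IPAVA flow. Because a listed primary outcome and half of the title question depend on this, it should be settled before the grades are analyzed.

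**What to change.** 1. In Section D, split the outcome. Report the change in room-air grade as total right-to-left flow and the change in 100% O2 grade as defect flow. Keep Valsalva readings separate. Draw no IPAVA conclusion from the room-air change alone or from the 100% O2 shunt fraction.
2. Base the resting IPAVA comparison on the within-subject room-air versus 100% O2 contrast, before versus after closure, analyzed as paired data. State the grading scale. Add a pre-specified sensitivity analysis limited to subjects whose pre-closure resting 100% O2 grade is low enough that defect flow cannot mask or saturate the room-air grade. Set that threshold from the scale: if the larger source determines the grade, the bias min(D, I) disappears only where one of the two is zero. State as limits that oxygen suppression of IPAVA flow may be incomplete and that differences of ordinal grades are approximate.
3. Report pre-closure exercise-stage grades as total shunt only. If too few subjects have an unmasked pre-closure resting grade, report IPAVA descriptively.

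The cost is a revision of the analysis text, using grades already planned. The downside is that the IPAVA comparison may rest on fewer subjects and may end up descriptive.

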Arterial blood will be taken at rest while subject is breathing room air and 100% O2 for 10-20 minutes to calculate shunt fraction (~30 min).

Subjects will be comprehensively screened for any cardiac abnormalities. Amount of blood flow travelling through the PFO/ASD and IPAVA will be graded using saline contrast echocardiography while the subject is breathing room air (PFO/ASD and IPAVA blood flow) and breathing 100% O2 (PFO/ASD blood flow only). Pulmonary artery pressure will also be measured using ultrasound. Intravenous blood draw, we will take 21mls (~2 Tablespoons) of iv blood (~1.25 hrs)

Subjects will perform pulmonary function, plethysmography and diffusing capacity (30min)

Subjects will undergo a hypercapnic breathing challenge (~1hr)

Visit 3b (If PFO/ASD **not physically closed/endothelialized** at 3 months per referring physician)

Subjects will undergo an intravenous blood draw, and we will take 21mls (~2 Tablespoons) of IV blood (30 min).

Visit 4a (PFO/ASD Physically Closed/Endothelialized) (~30 min) OR,

Visit 4b (PFO/ASD Not Physically Closed/Endothelialized) (~4.5 hrs)

Visit 4a (If PFO/ASD physically closed/endothelialized at 3 months per referring physician)

Subjects will undergo an intravenous blood draw, and we will take 21mls (~2 Tablespoons) of IV blood (30 min).

Visit 4b (If PFO/ASD **not physically closed/endothelialized** at 3 months per referring physician)

Subjects will be instrumented with a radial artery catheter by [name], MD. An esophageal temperature probe and an iv for saline contrast injections will also be placed. (~1hr).

Arterial blood will be taken at rest while subject is breathing room air and 100% O2 for 10-20 minutes to calculate shunt fraction (~30 min).

Subjects will be comprehensively screened for any cardiac abnormalities. Amount of blood flow travelling through the PFO/ASD and IPAVA will be graded using saline contrast echocardiography while the subject is breathing room air (PFO/ASD and IPAVA blood flow) and breathing 100% O2 (PFO/ASD blood flow only). Pulmonary artery pressure will also be measured using ultrasound. Intravenous blood draw, we will take 21mls (~2 Tablespoons) of iv blood (~1.25 hrs)

Subjects will perform pulmonary function, plethysmography and diffusing capacity (30min)

Subjects will undergo a hypercapnic breathing challenge (~1hr)

Description of Data Collection Procedures (timing of these procedures can be found in Table 1 and 2 below:

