We will use a published, well-established method (Duffin method) for assessing chemo sensitivity to carbon dioxide (MacKay et al., Adv Physiol Education, 2016). Subjects will be fitted with a nose-clip and breathe room air through a two-way rebreathing valve that can be directed between a filtered 6L non-diffusing bag filled with 7% CO2 and 93% O2 (medical grade) and room air. Ventilation, end tidal CO2 (PETCO2), end tidal O2 (PETO2) and saturation will be measured continuously throughout this testing (Medgraphics). To establish a baseline before hypercapnic testing using the modified rebreathing protocol, subjects will breathe room air for 5 min. Subjects will then be coached to hyperventilate by increasing the lung volume and frequency of breathing for 5 minutes to reach a target PETCO2 of ~20-25 mm Hg (~40-45 mm Hg is normal); this part of the test is required to reduce CO2 stores in the body. At 5 minutes the subject will be asked to take a full breath in and out then they will be switched to the bag filled with 7% CO2 and 93% O2 and will be coached to take 3 large breaths then resume normal breathing until: 1) their breathing increases so much that it becomes in tolerable and they signal to quit; 2) the PETCO2 = 55 mm Hg or 3) the rebreathing bag becomes deflated. Subjects will be informed of what to expect with this test prior to performing it, i.e they will be told that we will coach them through it and that when they start to breathe out of the bag they will initially have very little urge to breathe but as the rebreathing progresses they will have a very strong urge to breathe.

• Actigraphy (Days 2 & 4a OR 5b Exercise; Days 2-3a OR 4b NON-Exercise):

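### Non-exercise arm: as listed, the hypercapnic challenge precedes arterial sampling before closure and follows it after closure, so order and time in visit are confounded with closure

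*Combined protocol and SAP*

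**What the plan says.** All of this is in Section C, under NON-EXERCISE.

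**Before closure, two days.** Visit 1 lists consent and the Allen test, then contrast echo on room air and 100% O2 with the venous draw ("Intravenous blood draw, we will take 21mls (~2 Tablespoons) of iv blood (~1.25 hrs"), then lung function and DLCO. Visit 2 ("Visit 2 Pre PFO/ASD Closure Procedure (~3 hrs") lists four steps in this order:

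1. "Subjects will undergo a hypercapnic breathing challenge (~1hr"
2. "Subjects will be given an activity monitor and given instructions on how to use it (~30 min"
3. Radial artery catheter, with "An esophageal temperature probe and an iv for saline contrast injections will also be placed. (~1hr"
4. "Arterial blood will be taken at rest while subject is breathing room air and 100% O2 for 10-20 minutes (~30 min"

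**After closure, one day.** The visit is headed "Visit 3a (PFO/ASD Physically Closed/Endothelialized) (~4.5 hrs) OR", and Visit 4b has the same content for subjects not judged closed at 3 months. The listed order is line and probe, arterial samples, contrast echo with the 21 mL draw, lung function and DLCO, and the hypercapnic challenge last.

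The challenge is not a trivial stimulus. Its description says "Subjects will then be coached to hyperventilate by increasing the lung volume and frequency of breathing for 5 minutes", followed by rebreathing from a bag of 7% CO2 and 93% O2.

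The core temperature description says the esophageal reading is used to correct the blood gases, which ties it to arterial sampling. Section D compares pre with post by repeated measures ANOVA (AaDO2, core temperature) or paired t-test (markers, hypercapnic response). There is no comparison group and no term for order.

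**The concern.** A before-and-after study without controls attributes every systematic difference between the two occasions to the intervention. Its protection is to keep the measuring conditions the same. Here the non-exercise schedule changes them in the same way for every subject:

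- **AaDO2 and core temperature** follow a hyperventilation and rebreathing test before closure. After closure they do not, and they are taken earlier in the visit.
- **Hypercapnic response** is measured first in an uninstrumented subject before closure. After closure it comes last, after arterial cannulation, a nasal probe, two periods on 100% O2 and DLCO breaths.
- **Inflammatory markers** are drawn before any arterial line at Visit 1. In the main post-closure visit they are drawn after arterial and esophageal instrumentation.

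Section D names AaDO2 and TNFa as primary outcome variables, and the core temperature description calls that measure primary too. Neither planned test can separate an order or time-in-visit effect from an effect of closure.

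**Working it through.** **1. Do the listed steps account for the visits?** Stated durations, in hours:

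- Visit 1: 0.75 + 1.25 + 0.5 = 2.5 (stated about 2.5)
- Visit 2: 1.0 + 0.5 + 1.0 + 0.5 = 3.0 (stated about 3)
- Visits 3a/4b: 1.0 + 0.5 + 1.25 + 0.5 + 1.0 = 4.25 (stated about 4.5)

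They do, to within a quarter of an hour.

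**2. When does each measurement start, taking the lists as the order?**

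| Measurement | Before closure | After closure (3a/4b) |
|---|---|---|
| Arterial samples, core temperature | 1.0 + 0.5 + 1.0 = 2.5 h | 1.0 h |
| End of challenge to arterial samples | 0.5 + 1.0 = 1.5 h | no challenge beforehand |
| Hypercapnic challenge | 0 h | 1.0 + 0.5 + 1.25 + 0.5 = 3.25 h |
| Echo and marker block | 0.75 h into Visit 1, no line or probe | 1.0 + 0.5 = 1.5 h, after line, probe and 100% O2 |

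Arterial sampling is therefore 2.5 − 1.0 = 1.5 h earlier in the visit after closure, and the hypercapnic test is 3.25 h later. Section E asks for no food for 2 h before arrival. If nothing is eaten during the visit, the hypercapnic test is done at least 2 h after food before closure and at least 2 + 3.25 = 5.25 h after food post-closure.

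**3. Is the same true of the exercise arm?** In the visit text, no: Visits 4a, 5a and 6a repeat Visits 1, 2 and 3, as do 5b, 6b and 7b. That reading needs a caveat. The procedure descriptions place the hypercapnic test, actigraphy, VO2max and walk test on days 4a or 5b. Table 1 marks actigraphy and VO2max/walk at 4a and 5b.

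**4. What could an order effect do to the tests?** The documents give no value, so this is illustration only. Assume a shift of b standard deviations of the paired difference, no true closure effect, and a two-sided 5% paired t-test (sidedness is not stated). The rejection probability is P(|T| > t₀.₉₇₅,ₙ₋₁), with T noncentral t on n − 1 df and noncentrality b√n:

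| n | b = 0.2 | b = 0.5 |
|---|---|---|
| 8 | 7.8% | 23.2% |
| 10 | 8.8% | 29.3% |
| 20 | 13.6% | 56.5% |

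The n = 20 row would need all 20 recruits to be non-exercise subjects; their number is not stated. If half were, b = 0.2 in them averages about 0.1 over the 20, and the error rate is about 7.1%.

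**The case against.** The strongest reply is that the lists may not be a binding order. In the exercise arm the visit text gives the room-air bout and then the 40% O2 bout, while the procedure description says the bouts are randomized. Figure 2, meant to be read with the visit descriptions, is not available here. This stands as a limit: the listed order differs, but a difference in the order as carried out is not shown. It does not remove the point, because an order that is not fixed is not controlled either, and 3a and 4b list the same sequence.

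Four stronger readings are tempting and go too far.

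- **That the whole sequence is reversed.** Only the challenge and the arterial block change places. Echo still precedes lung function, and the rest comes from merging two days.
- **That the marker comparison is spoiled.** Every non-exercise subject also has a stand-alone 21 mL post-closure draw with no arterial line (Visit 4a or 3b), and the 63 mL total fits three draws. The offset is partial: that visit has no echo session, and the 3b draw precedes confirmed closure.
- **That the challenge contaminates AaDO2.** About 1.5 h separates the two at Visit 2, and nothing in the documents shows an effect lasting that long.
- **That earlier temperature readings favour the hypothesis of a lower core temperature.** This needs a similar clock start and a daytime rate of rise, and the documents give neither. The quoted 0.1 °C accuracy is no yardstick, since it belongs to the pill used only when the probe is not tolerated.

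It is also fair that only non-exercise subjects are affected, and that the food, caffeine, alcohol and exercise rules are the same before every visit.

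**Conclusion.** The point holds as a design confound, not as a demonstrated bias. As listed, arterial sampling and core temperature move from about 2.5 h to about 1.0 h into the visit and lose the preceding challenge. The hypercapnic test moves from 0 h to about 3.25 h and gains several preceding procedures. The marker draw is affected to a lesser degree. No text explains the change, and the analysis cannot adjust for it because order and closure coincide in every affected subject.

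This rests on the lists reflecting the intended order, on the stated approximate durations, and on temperature being read with the arterial samples. No size or direction can be given. It is worth correcting because matched conditions are what the exercise-arm visit text already provides, and matching them here is nearly free.

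**What to change.** In non-exercise Visits 3a and 4b, list the tests in this order: hypercapnic challenge, activity-monitor reminder, arterial line and probe, arterial samples with core temperature, contrast echo, lung function and DLCO. Keep the clock start and the 1.5 h challenge-to-sampling interval of Visit 2, using rest if the reminder takes less than 30 minutes.

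Take the marker sample at the same point in Visits 1, 3a and 4b: at IV placement, before saline, 100% O2, arterial line or probe. Visit 1 must change too, because it lists the draw with the echo block; moving only the post-closure draw would create a new mismatch. Visit 1 has no challenge, so the post-closure draw is best taken before the challenge. Placing the IV at the start of Visit 2 as well would keep the two challenges alike.

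State that the order is fixed, record start times, and reconcile the exercise-arm visit text with the procedure descriptions and Table 1.

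Cost: a wording change with no new procedure. The steps sum to 1.0 + 0.5 + 1.0 + 0.5 + 1.25 + 0.5 = 4.75 h, a quarter of an hour above the stated 4.5 h. One imperfection remains. Post-closure echo and lung function still share a day with the line and the challenge, so bubble score and lung function are not perfectly matched to Visit 1. For contrast echo this is eased because Table 2 also places one at Visit 2.
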